6.2. Adjustments for Covariates

Adjustment for covariates is not applicable.

6.3. Handling of Dropouts or Missing Data

Missing data will not be imputed.

Patients who withdraw from the study before receiving study drug will be replaced.

In the following situation, patients will be considered non-evaluable and may be replaced to ensure that enough patients complete 1 cycle of therapy at each dose level, unless accrual to that cohort has stopped due to a DLT:

1. Any patient who is discontinued from the study before completing 1 cycle of LY3164530 treatment unless they experience a DLT prior to withdrawal
2. Patients who are not evaluable for PK

6.4. Multicenter Studies

This is a multicenter, non-randomized, open-label study. Because of the limited sample size, endpoint analyses will not be conducted by enrollment center.

6.5. Multiple Comparisons/Multiplicity

No adjustments will be made for multiple comparisons unless otherwise specified.

6.6. Population for Analysis

Safety analyses will be conducted on all patients who have received at least one dose of LY3164530.

Pharmacokinetic analyses will be conducted on patients who have received at least one dose of LY3164530 and have sufficient samples collected to allow the estimation of LY3164530 PK parameters.

Pharmacodynamic analyses will be conducted on patients who have received at least one dose of LY3164530 and have sufficient samples collected to allow the assessment of pharmacodynamics.

6.7. Patient Disposition

A detailed description of patient disposition will be provided. It will include summaries of the following:

- The number and percentage of patients entered into the study, treated, as well as the number and percentage of patients discontinuing treatment and/or study.
- All patient discontinuations will be documented, and the extent of each patient's participation in the study will be reported. Data on patient discontinuation from study

drug and study (overall and by reason for discontinuation) will be collected. If known, reason(s) for discontinuation will be given. Discontinuations due to AE or death will be summarized with cause of death further partitioned into AE, study disease, or other cause and summarized.

- All clinically relevant and programmatically identifiable protocol deviations will be summarized by pre-determined categories (for example, inclusion/exclusion criteria, non-compliance with protocol procedures, drug dosage/intervention, use of excluded treatments, informed consent/assent process, continuing after meeting withdrawal criteria, or other).

All patients entered into the study will be accounted for in the summary disposition tables. Patients entered into study are patients who signed main informed consent. The number of patients who do not qualify for analysis, who die, or who discontinue before treatment begins will be specified.

6.8. Patient Characteristics

Patient characteristics for the treated population will include a summary of the following:

- Patient demographics, including age, sex, screening height and weight, and screening body mass index, reported using descriptive statistics
- Baseline disease characteristics, including initial diagnosis and Eastern Cooperative Oncology Group (ECOG) performance status, summarized by presenting frequency counts and percentages
- Prior disease-related therapies if known, including dose, best response, duration of response, date of progression and etc.
- Concomitant medications.

6.9. Treatment Compliance

LY3164530 will be administered intravenously at the investigational site, under the direction of the investigator. As a result, a patient's compliance with study drug administration is ensured.

Potential discontinuation of a patient due to study noncompliance (not attending the scheduled visits; see Protocol Attachment 1) will be presented overall as well as for each cycle.

6.10. Concomitant Therapy

Concomitant medications will be summarized for the safety population using the World Health Organization (WHO) preferred nomenclature. The numbers and percentages of patients reporting concomitant therapies will be provided overall, by type of therapy (surgery, radiotherapy, or systemic therapy), and by drug name.

Prior therapies, including systemic, radiotherapy, and cancer surgeries will be summarized by cohort and overall for all enrolled patients. The Lilly WHO Drug Version Dec 2012 B2 or higher will be used to code therapy.

6.11. Efficacy Analyses

The study was not designed to make an efficacy assessment. However, any tumor response data and duration of treatment will be tabulated.

6.12. Bioanalytical and Pharmacokinetic/Pharmacodynamic Methods

6.12.1. Pharmacokinetic/Pharmacodynamic (PK/PD) Analyses

Pharmacokinetic analyses will be conducted on patients who have been exposed to study drug and have had samples collected.

Pharmacokinetic parameter estimates for LY3164530 will be calculated by standard noncompartmental methods of analysis.

The primary parameters for analysis will be C_{max} , $AUC_{0-t_{last}}$, and $AUC_{0-\infty}$ of LY3164530. Other noncompartmental parameters, such as $t_{1/2}$, CL, and volume of distribution (V), may be reported. Additional exploratory analyses will be performed if warranted by the data, and other validated PK software programs may be used if appropriate and approved by Lilly Global PK/PD management. The version of any software used for the analysis will be documented and the program will meet the Lilly requirements of software validation.

Pharmacokinetic parameter estimates will be evaluated to delineate effects of dose proportionality and temporal linearity. Log-transformed C_{max} and AUC estimates will be assessed to estimate ratios of geometric means and the corresponding 90% confidence intervals (CIs).

Provided that the data allows, PD and immunogenicity data from all patients may be analyzed using linear and/or nonlinear fixed and mixed effects models as appropriate. Pharmacodynamic and immunogenicity data will be summarized by dose, drug concentrations, and time from dose. Potential PD markers and immunogenicity versus time data will be presented graphically for each patient and summarized by dose. Absolute and/or percent change from baseline for the PD markers may also be evaluated. Data may be log-transformed prior to summarizing if necessary. The interpatient and inpatient variability of the PD markers and immunogenicity responses may also be assessed where appropriate. Baseline measurements may be evaluated as potential covariates to assess their relationship to relevant PD responses.

In addition to a standard noncompartmental assessment, and provided that the data allows, the LY3164530 concentration-time data may be evaluated by model-based approaches as warranted. Additional analyses, such as exposure-response modeling using the efficacy endpoints, may also be explored.

Additional exploratory analyses may be performed if warranted by the data.

6.12.2. Biomarker Analyses

Protocol Sections 5.3.4 and 8.2.3 provide a description of the biomarker samples that may be collected and the rationale for their collection in the study.

Exploratory biomarker assessments in this study will focus on identifying markers and/or marker signatures that may indicate the patients most likely to respond or be resistant to LY3164530. In archived and/or pre-treatment tissue samples, biomarker data related to the MET and EGFR pathways and cancer pathobiology may be analyzed to assess any potential associations with response to LY3164530. These analyses may include, but are not limited to, MET and EGFR protein expression, circulating biomarkers (for example, TGF α , HGF, extracellular cleaved domain of MET [MET ECD]), somatic mutation status, and/or copy number variations of MET and EGFR and pathway-related genes (for example, KRAS, BRAF) or genes related to cancer pathobiology. In addition, tumor sample based gene signature(s) may be defined and evaluated to explore whether they are associated with response to LY3164530.

In all analyses, adjustments may be made to account for other baseline patient characteristics, safety, and PK/PD data. Unless otherwise stated, statistical analyses results will be considered exploratory and will not consider multiple comparison adjustments. In the event of emergence of important and relevant scientific findings, this SAP may be updated to allow further analyses on biomarkers and antitumor activities.

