An interim analysis of the LY3164530 PK data was conducted from all of the 15 patients who received at least 1 dose of LY3164530 administered as a 1 or 2-hour infusion once every 2 weeks (Q2W) across the dose range of 300-1250 mg. Dose-dependent increases in the systemic exposure (AUC, C_{max}) of LY3164530 following single and multiple doses were observed. A minor amount of accumulation in serum was observed within Cycle 1 and between Cycles 1 and 2 of treatment after 1000 mg Q2W (mean accumulation ratio of 1.1 within and between cycles). The LY3164530 systemic clearance (CL) decreased by approximately 2-fold on average when the dose was escalated from 600 mg to 1000 mg, indicating the saturation of cell-surface receptors by LY3164530 and a slower non-receptor-mediated clearance predominating at doses >600 mg. While a more rapid receptor-mediated clearance (ie, target mediated drug disposition [TMDD]) predominates at low doses (ie, ≤ 600 mg). In addition, the LY3164530 exposure following 1000 mg Q2W appears to be in an exposure range expected to achieve biological effects based on the nonclinical MKN45 xenograft PK/PD model estimates for the MET and EGFR half maximal effective serum concentrations (EC_{50}) values. The LY3164530 maximum serum concentration (C_{max}) after 1000 mg in Cycles 1 and 2 is greater (mean C_{max} range: 295-394 $\mu\text{g/mL}$) than both the MET EC_{50} (79.5 $\mu\text{g/mL}$; 0.4 μM) and EGFR EC_{50} (7.95 $\mu\text{g/mL}$; 0.04 μM) concentrations. The average LY3164530 serum concentration over the dosing interval ($C_{av,\tau}$) during Cycles 1 and 2 is also greater (mean $C_{av,\tau}$ range: 102-132 $\mu\text{g/mL}$) than the MET EC_{50} and EGFR EC_{50} . However, the minimum serum concentration over the dosing interval ($C_{min,\tau}$) of LY3164530 following 1000 mg in Cycles 1 and 2 (mean $C_{min,\tau}$ range: 19-49 $\mu\text{g/mL}$) is lower than the MET EC_{50} (79.5 $\mu\text{g/mL}$), which is the desired concentration to maintain throughout the dosing interval in order to maximize the biological activity of LY3164530.

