8.2.2.2. Pharmacodynamic Samples

At the visits and times specified in [Attachment 3](#), serum and plasma samples will be collected. The effect of LY3164530 on MET and EGFR pathway-specific targets may be explored to determine changes in potential biomarkers such as circulating levels of the MET ligand HGF,

EGFR ligands (eg, EGF, TGFalpha), MET/ECD, and EGFR/ECD. These samples may be used for exploratory research on new biomarkers related to the MET/HGF and EGFR pathway. In addition, exploratory samples to assess proteomic panel may be collected. A maximum of 3 timepoints may be removed per dosing schedule during the study if warranted and agreed upon between both the investigator and Lilly.

Bioanalytical samples collected to measure PD biomarkers will be identified by the patient number (coded) and retained for a maximum of 15 years following last patient visit for the study at a facility selected by the Sponsor. Supplies and detailed instructions required for the collection, handling, and shipment of the patients' samples will be provided by the Sponsor. The samples will be analyzed at a laboratory designated by the Sponsor.

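### The exploratory marker-response analyses may be adjusted for safety and PK/PD data measured after dosing, which can weaken, remove, strengthen or reverse the association sought

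*SAP*

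**What the plan says.** The biomarker work in SAP 6.12.2 aims at "identifying markers and/or marker signatures that may indicate the patients most likely to respond or be resistant to LY3164530". The source material is mainly taken before treatment: "In archived and/or pre-treatment tissue samples, biomarker data related to the MET and EGFR pathways and cancer pathobiology may be analyzed". The adjustment rule follows: "In all analyses, adjustments may be made to account for other baseline patient characteristics, safety, and PK/PD data". Protocol 10.9 carries the same sentence.

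Neither section restricts the adjustment to pre-dose values, names a model, or asks for an estimate without these terms. Reading the word baseline as covering the whole list does not work: drug exposure has no pre-dose form, and toxicity accrues on treatment. PD does have a predose sample (protocol Attachment 3), but nothing limits the sentence to it.

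SAP 6.2 says the opposite of 6.12.2: "Adjustment for covariates is not applicable".

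**The concern.** A marker meant to show who responds is known before the first dose. Its association with response includes everything that happens afterwards because of it. If a later variable on that path enters the model, the coefficient no longer measures that association. If the later variable also shares an unmeasured cause with response, conditioning on it adds a non-causal component.

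The documents make such paths plausible for each type of covariate:

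- **PD.** Protocol 8.2.2.2 describes the samples by their purpose: "The effect of LY3164530 on MET and EGFR pathway-specific targets may be explored to determine changes in potential biomarkers". The analytes include HGF and "EGFR ligands (eg, EGF, TGFalpha), MET/ECD, and EGFR/ECD". SAP 6.12.2 also names TGF alpha, HGF and MET ECD as candidate biomarkers, so a marker could be adjusted for its own on-treatment value.
- **PK.** The interim PK summary in protocol Section 5 reports that "a more rapid receptor-mediated clearance (ie, target mediated drug disposition [TMDD]) predominates at low doses", which it defines as 600 mg or less.
- **Safety.** Protocol 7.2.4.2 treats rash as a recognised effect of EGFR inhibition. Safety is also an outcome in the biomarker objective (protocol 5.2.3, SAP 4.3), yet it is an allowed covariate in all analyses. Patients who benefit may stay on drug beyond the planned two cycles (protocol 6.2), so cumulative toxicity can itself follow from response.

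At stake is the reading of an exploratory objective that could influence later patient selection.

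**Working it through.** The plan gives no effect size, marker prevalence or response rate for these analyses, so it has no figure of its own to reproduce. Every coefficient below is assumed.

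**1. Linear path model, standardised.** Let M be the marker, P the post-dose variable, Y the response, and U an unmeasured cause of P and Y that is independent of M. The paths are a (M to P), b (P to Y), c (M to Y directly), g (U to P) and d (U to Y).

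- Total effect of M: c + ab.
- With P standardised, its variance given M is 1 - a². The coefficient of M adjusted for P is c - adg/(1 - a²).

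Inputs: a = b = 0.5, c = 0.

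- Total: 0.5 × 0.5 = +0.25 SD.
- Adjusted, no shared cause (g = d = 0): 0.
- Adjusted, g = d = 0.3: -(0.5 × 0.3 × 0.3)/0.75 = -0.06 SD.
- Adjusted, g = d = 0.5: -(0.5 × 0.5 × 0.5)/0.75 = -0.167 SD.

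With a positive direct effect c, the adjusted value is c - 0.06 or c - 0.167. A reversal therefore disappears once c exceeds 0.06 or 0.167 respectively.

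**2. Logistic version.** P = aM + gU + e, with M, U and e of unit variance, and logit(response) = b0 + cM + bP + dU. On the linear predictor the M coefficient is c + ab without P and c - adg/(g² + 1) with P. Odds ratios (OR) per SD of marker come from 400,000 simulated patients. Detection (p < 0.05) comes from 1,500 simulated trials of 50 patients, the approximate total in protocol 10.1. Trials with fewer than 3 responses or a failed fit were dropped, leaving 1,494 to 1,499 trials per row. The assumed response rate is 20%.

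| Assumed structure | Linear predictor, without P → with P | OR, without → with | Detection, without → with |
|---|---|---|---|
| Full mediation (a=0.8, b=1, c=0) | 0.80 → 0.00 | 2.01 → 1.00 | 41% → 3% |
| Partial mediation (a=0.8, b=0.7, c=0.3) | 0.86 → 0.30 | 2.22 → 1.35 | 49% → 8% |
| Mediation plus shared cause (a=b=g=d=0.8, c=0) | 0.64 → -0.31 | 1.60 → 0.75 | 20% → 6% |
| Marker lowers exposure (a=-0.8, b=0.7, c=0.3) | -0.26 → 0.30 | 0.79 → 1.35 | 8% → 7% |
| Marker lowers exposure, strong direct effect (a=-0.5, b=0.5, c=0.8) | 0.55 → 0.80 | 1.70 → 2.23 | 25% → 43% |
| P unrelated to marker (a=0, b=0.7, c=0.6) | 0.60 → 0.60 | 1.74 → 1.82 | 29% → 30% |

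The pattern of ORs is the same at assumed response rates of 10% and 30%. Under full mediation, for example, the OR is 2.08 → 1.02 at 10% and 1.97 → 1.00 at 30%. The small shift in the last row is the usual non-collapsibility of the odds ratio, since the linear predictor does not move.

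**3. Reading.** Loss of the association requires the marker to act through P. Reversal requires a shared cause or an opposing path. A receptor-driven exposure variable can push the estimate upward.

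**The case against.** The sentence permits adjustment and does not plan it. Results are labelled exploratory without multiplicity control, and SAP 6.11 says the study was not designed to assess efficacy. Harm needs a post-dose covariate to be chosen, to lie on the path, and to be reported without the unadjusted figure. The documents establish none of these. This stands, and it sets the weight of the point.

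The mechanism also has limits. On escalation from 600 mg to 1000 mg the protocol reports a fall in clearance of about 2-fold, "indicating the saturation of cell-surface receptors by LY3164530", with non-receptor clearance predominating above 600 mg. The step from whole-body receptor clearance to tumour MET/EGFR expression is an inference. No section says that rash depends on tumour marker status or mediates response. This stands too.

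A PK-adjusted model can be legitimate. Dose is not randomised, clearance changes with dose, and doses are reduced or omitted, so the association at a given exposure is a fair question. Protocol 10.7 and SAP 6.12.1 already provide for exposure-response modelling. This argues against banning PK/PD terms, but not against keeping them out of the main estimate.

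Overfitting is not a separate argument against post-dose terms. At an assumed 10% to 20% response rate, 50 patients give 50 × 0.10 = 5 to 50 × 0.20 = 10 responders, which limits baseline covariates just as much.

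What the objection does not answer is that the exploratory label excuses low power and unadjusted multiplicity. It does not excuse leaving open which quantity is estimated.

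**Conclusion.** The point holds as a caution about a stated, optional method. Both documents allow marker-response analyses to condition on variables that arise after dosing and may lie between marker and response, and neither asks for an estimate without them. In the linear illustration, +0.25 SD becomes about -0.06 to -0.17 SD. That rests on assumed paths of 0.5, no direct marker effect and shared-cause paths of 0.3 to 0.5. Other assumed structures weaken or strengthen the association, or leave it nearly unchanged.

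A reader might infer that a truly predictive marker will be lost or reversed in this trial. The documents do not support that. The adjustment may never be used, the causal paths are plausible but not shown, and without a control arm the trial cannot separate predictive from prognostic markers.

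The conflict between SAP 6.2 and 6.12.2 is a drafting inconsistency that stands whatever one makes of the causal argument. Severity is low, and the primary RP2D objective is unaffected.

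**What to change.** In SAP 6.12.2 and protocol 10.9, replace the adjustment sentence with text to this effect:

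- The main marker-response estimate is unadjusted, or adjusted only, and sparingly, for variables fixed before the first dose (for example tumour type or prior therapy) plus assigned dose and schedule.
- Safety, PK and PD are analysed as outcomes of the marker.
- Any model with post-dose PK, PD or safety terms is a separately labelled secondary exposure-response or mediation analysis, shown beside the main estimate.
- Results are described as marker-response associations, not predictive effects.

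Reword SAP 6.2 so that it excepts, or points to, the adjustments allowed in 6.12.2. The SAP describes only the Days 1 and 15 regimen, so schedule has to be introduced there as a covariate.

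The cost is a few sentences in each document and, where a post-dose model is wanted, one extra model to report. No data collection changes.

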6.13. Safety Analyses

All patients who receive at least 1 dose of LY3164530 will be evaluated for safety and toxicity. Adverse event (AE) terms and severity grades will be assigned by the investigator using National Cancer Institute Common Terminology Criteria for Adverse Events (NCI CTCAE) Version 4.03.

Safety analyses will include summaries of the following:

- Adverse events, including severity and possible relationship to study drugs
- Dose delays and dose adjustments
- Laboratory values
- Vital signs
- Dose-limiting toxicities at each dose level
- Electrocardiogram readings
- Deaths on treatment and within 28 +/- 5 days of treatment discontinuation

Hospitalizations and transfusions during the study treatment period or during the 28 +/- 5 days - day postdiscontinuation follow-up period will be summarized.

Dose Limiting Toxicity

Dose-limiting toxicity is defined as an AE during Cycle 1 that is considered by the investigator to be at least possibly related to LY3164530 and fulfills any one of the following criterion using the NCI CTCAE Version 4.03:

- \geq Grade 3 non-hematological toxicity. Exceptions will be made for:

- nausea, vomiting, diarrhea, and constipation that can be controlled with treatment. Grade 3 and Grade 4 nausea, vomiting, or diarrhea should be considered DLTs if persisting more than 48 hours despite supportive intervention.
 - Grade 3 rash that resolves with treatment to \leq Grade 2 within 8 days
 - Grade 3 or 4 asymptomatic electrolyte abnormalities that respond to standard treatment
 - Grade 3 elevations of ALT and/or AST lasting fewer than 8 days, without evidence of other hepatic injury, in the setting of preexisting hepatic metastasis. Baseline elevation of these values may not be considered a DLT if agreed by the study investigator and Lilly CRP/CRS.
- Grade 4 neutropenia or leukopenia, of >7 days duration.
 - Grade 4 thrombocytopenia of any duration.
 - Grade 3 thrombocytopenia with bleeding.
 - Any febrile neutropenia.
 - Any other significant toxicity deemed by the primary investigator and Lilly clinical research personnel to be dose limiting (eg, any toxicity that is possibly related to the study drug that requires the withdrawal of the patient from the study during Cycle 1).

DLT-Equivalent Toxicities

A DLT-equivalent toxicity is defined as an AE occurring in Cycle 2 and beyond that would have met the criteria for a DLT if it had occurred during Cycle 1.

Dose Escalation Method

Dose escalation will be driven by an mTPI method (Ji and Wang 2013) ([Appendix 1](#)). A 3+3 design is commonly used in Phase 1 trials due to its simple, intuitive, and pre-specified escalation rules. However, the 3+3 method has been criticized for being conservative because the method is dictated by the observed DLT rate without acknowledging the variability arising from small cohort size.

Like the 3+3 design, the mTPI method incorporates pre-specified escalation rules. In contrast, the mTPI method is based on quantitative models that incorporate uncertainty into the decision rules, thereby allowing more aggressive dose escalation. In the mTPI method, the number of patients in each cohort is not fixed, but a minimum of 3 patients are required for this study at each dose (unless the rule in the table indicates to deescalate the dose due to unacceptable toxicity [DU]). If 3 to 6 patients are enrolled in a cohort, the escalation rule parallels a traditional 3+3 design. However, the stay/de-escalation rule of the mTPI is more aggressive than the 3+3 design. For instance, with 2 to 3 DLTs per 6 patients enrolled, the mTPI would recommend staying at the current dose, whereas the 3+3 design would recommend de-escalation. [Figure JNBA.6.1](#) provides the mTPI escalation rules for any cohort size up to 20 patients.

In [Figure JNBA.6.1](#), the number of patients dosed at a given dose level are shown in the columns (x-axis), while the number of DLTs experienced are shown in the rows (y-axis). The rules in this figure will be used for each dose level evaluated; the patient numbers and DLTs do not carry over from cohort to cohort. By locating the intersection of the number of patients dosed and the number of DLTs, 1 of 4 pre-defined rules is used:

- E: Escalate the dose
- S: Stay at the same dose
- D: Deescalate the dose
- DU: Deescalate the dose due to unacceptable toxicity. The dose cannot be re-escalated to this dose level at a future point in the escalation.

If agreed upon by the investigators and Sponsor (for instance, if PK/PD data suggest that increasing the dose further is not expected to yield additional benefit), a more conservative rule may be applied. For instance, if the rule indicates “E” to escalate, the dose may remain at the current dose level or be deescalated to a lower level.

As shown in [Figure JNBA.6.1](#), if 1 of 3 patients experiences a DLT, the decision (located in column 3 row 1) is “S”, stay at the same dose. Therefore, the next patient must be treated at the same dose level. If 1 of 6 patients experience a DLT, the decision (located at column 6 row 1) is “E”, escalate the dose. However, if 2 of 3 patients experience a DLT the decision is “D” and the dose must be deescalated.

In the mTPI, the cohort size is not fixed. However, each cohort in this study will contain a minimum of 3 patients, unless the escalation rules dictate that the dose should be deescalated due to unacceptable toxicity (“DU”). Doses can be escalated, deescalated, and re-escalated following the rules in [Figure JNBA.6.1](#). If the dose decision was “DU,” the dose cannot be re-escalated to that level.

This study is designed to identify a dose level with a dose-limiting target toxicity rate of 30%. In reality, the exact target toxicity rate is almost never achieved for a dose. To this end, instead of using a single target rate, the mTPI method considers an equivalence interval (EI) around the target toxicity rate. For this study, the EI is calibrated to be (28.7%, 30.1%), resulting in the rules in [Figure JNBA.6.1](#). If the observed toxicity rate exceeds 40% and the model is still recommending “S”, the Sponsor, in discussion with the investigators, may choose to deescalate.

		Number of patients treated at current dose																			
		1	2	3	4	5	6	7	8	9	10	11	12	13	14	15	16	17	18	19	20
Number of DLTs	0	E	E	E	E	E	E	E	E	E	E	E	E	E	E	E	E	E	E	E	E
	1	D	S	S	S	S	E	E	E	E	E	E	E	E	E	E	E	E	E	E	E
	2		DU	D	S	S	S	S	S	S	S	E	E	E	E	E	E	E	E	E	E
	3			DU	DU	D	S	S	S	S	S	S	S	S	S	S	E	E	E	E	E
	4				DU	DU	DU	D	D	S	S	S	S	S	S	S	S	S	S	S	S
	5					DU	DU	DU	DU	DU	D	S	S	S	S	S	S	S	S	S	S
	6						DU	DU	DU	DU	DU	D	S	S	S	S	S	S	S	S	S
	7							DU	D	S	S	S	S	S	S						
	8								DU	D	S	S									
	9									DU	S										
	10										DU										
	11											DU									
	12												DU								
	13													DU							
	14														DU						
	15															DU	DU	DU	DU	DU	DU
	16																DU	DU	DU	DU	DU
	17																	DU	DU	DU	DU
	18																		DU	DU	DU
	19																			DU	DU
	20																				DU

E = Escalate to the next higher dose
 S = Stay at the current dose
 D = De-escalate to the next lower dose
 U = The current dose is unacceptably toxic
 Target DLT rate = 30%
 Equivalence interval = (28.7%, 30.1%)

Figure JNBA.6.1. Dose-finding spreadsheet of the modified toxicity probability interval method.

The beginning dose level will be 300 mg. The dose will be escalated by a maximum increment of 100%. If the beginning dose level is determined to be unacceptably toxic, a -1 dose level may be explored.

The exact increment will be determined by the investigators and Lilly CRP/CRS, and may be less than the maximum increment allowed in the protocol. Safety data will be the primary criteria for both the decision to dose-escalate and for selecting the dose to be administered in the next cohort. In addition, if available at the time of the dose escalation decision, PK (maximum plasma concentration [C_{max}], area under the plasma concentration-time curve [AUC], and CL) and/or PD results will be used as secondary/supporting data for dose escalation. No dose escalation can occur without prior discussion and agreement between the investigator and the Lilly CRP or CRS; the decision will be documented in writing. Inpatient dose escalations are not permitted.

In Cohort 1 only, the first patient is required to complete a full cycle (28 days) before subsequent patients can be dosed. Subsequent patients in Cohort 1 can be dosed concurrently. Beginning with Cohort 2, patients within a cohort can be dosed concurrently.

The decision to stop dose escalation will be primarily driven by the appearance of DLTs and the rules in [Figure JNBA.6.1](#). However, if PK/PD data suggest that increasing the dose further is not expected to yield additional benefit, escalation may cease.

